### 2.4.3 Exploratory Endpoints

- Change in antigen-specific T cell responses in peripheral blood from baseline (screening visit) to post-RP (9 weeks post-RP visit) assessed by using a T cell proliferation assay, and interferon gamma (IFN- $\gamma$ ) immunospot (ELISPOT) assays. In a limited number of patients we will also assess for antigen-specific T cells in tumor infiltrating lymphocytes isolated from the RP as fresh tissue is available.
- Development of and changes in humoral immune responses in the periphery following treatment. This will be evaluated by testing serum with methods such as:
  - Measurement of antibodies to PSA,TAA and the viral vector using peptide/protein arrays or standard ELISA assays.
- To characterize the frequency of circulating B and T cells induced by neoadjuvant PROSTVAC or ipilimumab or the combination in patients with localized prostate cancer by flow cytometry. In a limited number of patients we will also assess for antigen-specific T cells in tumor infiltrating lymphocytes isolated from the RP as fresh tissue is available.
- T-cell receptor (TCR) repertoire sequencing following restimulation with prostate specific tumor-associated antigens and viral vector specific antigens to evaluate clonality of T-cell responses in the periphery. TCR repertoire in the tumor may also be evaluated in prostate biopsy samples to allow correlation with responses in the periphery.
- Change in PD-L1 expression by IHC assessment following neoadjuvant PROSTVAC or ipilimumab or the combination
- The clinical benefit of neoadjuvant PROSTVAC or ipilimumab or the combination as measured by:
  - Proportion of patients with a PSA response ( $\geq 30\%$  PSA decline) at the time of RP.
  - Proportion of patients with pathologic complete response (pT0) or near complete response at the time of RP.

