### 7.1.3 PSA

The utility of a decline in PSA as a marker of response to neoadjuvant therapies is not well defined. However, the proportion of patients with PSA response, defined as  $\geq 50\%$  PSA decline, will be reported.

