  - Measurement of cytokines, chemokines or cancer biomarkers by Luminex multiplex analysis will be summarized by descriptive statistics for continuous variables at each timepoint for each arm. Furthermore, repeated measure ANOVA methods with a mixed model approach to allow for a varying number of follow-up measurements will be applied. The specific comparison of change between baseline and any specific post-baseline time point will be tested also using linear contrast statements.
  - PD-L1 expression, by IHC assessment, will be scored on a 0-3 scale (0=0-5% staining, 1=6-33% staining, 2=34-66% staining, 3=67-100% staining). For each subject, the change in PD-L1 expression score following neoadjuvant therapy will be calculated for exploratory characterization of the impact on PD-L1 in localized prostate cancer. Descriptive statistics for categorical measurements will be used to summary the PD-L1 expression change for each location. Furthermore, univariate analysis (proportion test) will be applied to explore the PD-L1 expression score change between locations.
- In order to assess the clinical impact of neoadjuvant treatment with PROSTVAC, ipilimumab, or the combination or PROSTVAC and ipilimumab:

- The proportion of patients who achieve a  $\geq 30\%$  decline in PSA at the time of RP will be reported with 95% confidence intervals.
- The proportion of patients with pathologic complete response (pT0) at the time of RP will be reported with 95% confidence intervals.
- T-cell receptor (TCR) repertoire sequencing following re-stimulation on T cells in vitro with prostate specific, tumor associated antigens and vector specific antigens to evaluate clonality of T-cell responses in the periphery. The responses in the tumor may also be evaluated in prostate biopsy samples to allow correlation with responses in the periphery. For each individual treatment, the change in tumor-infiltrating TCR between pre-treatment and post-prostatectomy after treatment will be assessed by calculating the number of unique clonotypes comprising the top 25th percentile of cumulative reads after sorting by clone abundance. Repertoire change between sequencing experiments will be measured using Morisita's distance.

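### Section 8.5.3 summarises PD-L1 only as change in a 0-3 score and PSA only as a ≥30% responder proportion; adding continuous per-arm summaries would recover discarded information at little cost

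*Combined protocol and SAP*

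**What the plan says.** **PD-L1.** Section 8.5.3 scores staining in four bins: "PD-L1 expression, by IHC assessment, will be scored on a 0-3 scale (0=0-5% staining, 1=6-33% staining, 2=34-66% staining, 3=67-100% staining"). For each man, "the change in PD-L1 expression score following neoadjuvant therapy will be calculated for exploratory characterization of the impact on PD-L1 in localized prostate cancer". The summary is categorical: "Descriptive statistics for categorical measurements will be used to summary the PD-L1 expression change for each location". The only test named compares tissue locations, not arms: "univariate analysis (proportion test) will be applied to explore the PD-L1 expression score change between locations".

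**PSA.** Section 2.4.3 lists as an exploratory endpoint "Proportion of patients with a PSA response", with response set at a fall of at least 30% by the time of surgery. Section 8.5.3 gives the whole analysis: the proportion with that "decline in PSA at the time of RP will be reported with 95% confidence intervals". No test is named. Section 7.1.3 cautions that "The utility of a decline in PSA as a marker of response to neoadjuvant therapies is not well defined".

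**Data available.** PSA is drawn at screening (6.1.1.2) and before prostatectomy (5.3, 6.1.4, Tables 3 and 4), so each man with both samples has a continuous change. For PD-L1 the bins are defined by percent staining, but the text does not say that the percentage itself is recorded.

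**Other markers.** Section 8.5.3 summarises Luminex markers as continuous variables with mixed models and takes log2 pre/post differences for antibody arrays. Section 8.5.2 treats flow cytometry changes as continuous. No reason is given for handling PD-L1 and PSA differently.

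**The concern.** Both quantities have an underlying continuous scale, and the plan analyses them only after cutting it. Movement inside a PD-L1 bin disappears, however large, and movement of one percentage point across a boundary counts as a full grade. For PSA, a fall just short of 30% cannot be told apart from a rise.

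PD-L1 change is a stated exploratory objective, and PSA is one of only two clinical-benefit measures (section 2.3). With about 13 men per arm, a moderate change shared by most of them could be almost invisible in the planned output although the samples contain it.

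**Working it through.** **1. Stated figures.** The plan gives no power, SD or distribution for PD-L1 or PSA. The figure of 13 per arm comes from section 8.2 and concerns the CD3+ response rate. It reproduces: the exact 90% interval for 3/13 is 6.6% to 49.5%, and 39/(1 − 0.07) = 41.9, rounded up to 42. It is used below only as the likely number of men per arm.

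**2. PD-L1 bins.**

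| Before → after | Change in staining | Scores | Change in score |
|---|---|---|---|
| 34% → 66% | 32 points | 2 → 2 | 0 |
| 6% → 33% | 27 points | 1 → 1 | 0 |
| 33% → 34% | 1 point | 1 → 2 | +1 |
| 5% → 6% | 1 point | 0 → 1 | +1 |

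**3. PSA in one arm of 13.** In the limiting case all 13 men fall exactly 20%. The planned result is 0/13, with exact 95% upper limit 1 − 0.025^(1/13) = 24.7%. An arm in which every PSA rose gives the same result.

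Now let the fall vary, with an assumed SD of 0.25 for the log ratio.
- Share passing the cut: Φ[(ln 0.70 − ln 0.80)/0.25] = Φ(−0.53), about 30%. That is about 4/13, exact 95% CI 9.1% to 61.4%.
- With no true fall: Φ(ln 0.70/0.25) = Φ(−1.43), about 8%. That is about 1/13, CI 0.2% to 36.0%. The two intervals overlap widely.
- Geometric mean ratio of 0.80: half-width on the log scale 2.179 × 0.25/√13 = 0.151, so the 95% CI is 0.80 × exp(∓0.151) = 0.69 to 0.93. At SD 0.15 it is 0.73 to 0.88, and at SD 0.35 it is 0.65 to 0.99.

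**4. Information kept by a binary cut.** For a normal variable cut so that a share q responds, the fraction kept is φ(z_q)²/[q(1 − q)].

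| q | Fraction kept | 13 men act like |
|---|---|---|
| 50% | 0.64 | 8.3 |
| 25% | 0.54 | 7.0 |
| 10% | 0.34 | 4.4 |
| 5% | 0.22 | 2.9 |

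**5. Does this become a loss of power?** The plan has no between-arm test here, so this step is hypothetical. It borrows the 13 v 26 split and alpha 0.10 of the CD3+ comparison (8.2, 8.5.1), taken as two-sided, and uses an uncorrected proportion test. Assumptions: SD of log PSA change 0.15/0.25/0.35; PD-L1 logit-normal with median baseline 2% to 20%, logit SD 1.0 between men and 0.8 for change. Simulated power:

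| Effect in the combination arm | Continuous | Cut |
|---|---|---|
| PSA: every man falls 20% (t test v ≥30% cut) | 99/83/58% | 67/58/40% |
| PSA: 20% of men fall 50%, the rest unchanged | 55/39/28% | 72/44/26% |
| PD-L1: odds of staining doubled in all men (rank-sum on percent v any rise in score) | 74–78% | 41–49% |
| PD-L1: odds × 10 in 25% of men, the rest unchanged | 31–35% | 37–40% |

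The continuous measure is clearly better for a shared shift. For a minority of strong responders the advantage vanishes or reverses.

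**The case against.** **No planned test loses power.** PSA is estimated with an interval and not tested, and the one PD-L1 test compares locations. A reader might infer that the plan suffers a large loss of power, or always gives up 13 percentage points or more. The documents support neither reading. The 13-per-arm, 13 v 26 and alpha 0.10 settings belong to CD3+, and step 5 shows that the direction depends on the pattern of response. This objection stands.

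**A minority pattern is plausible.** The background in 1.3.3 mostly reports PSA falls of at least 50% in a minority: 2 of 14 in the first ipilimumab trial, and 13.1% v 5.3% in the phase III trial. An exception is 5 of 9 with ipilimumab plus PROSTVAC. These are advanced-disease data, so they do not settle what happens before surgery, but they are a good reason to keep the responder proportion. With Fisher's test in place of the uncorrected test, the cut's advantage for 20% responders mostly goes (51% and 35%, against 55% and 39% for the t test, at SD 0.15 and 0.25). Even then no large loss appears.

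**PD-L1 percentages may be fragile.** Percent read by eye is less reproducible than a four-level score, and the simulations model no separate reading error. If half the men had zero staining, simulated power on percent would be only 41–44%, against 26–31% for the cut. This limits the gain but does not remove the case for recording the percentage.

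**The endpoints are exploratory.** No decision rests on them, and 7.1.3 already cautions about PSA. That sets the severity. It does not explain why a PSA change already measured should go unreported.

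**Conclusion.** The point holds as one of lost information and precision, and it is minor. The bin and threshold arithmetic follows directly from the text. For PSA the exact statement is that a fall short of 30% is pooled with stable and rising values as non-response; the plan does not record it as no change.

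The size depends on assumptions. Under normality a single cut leaves 13 men worth about 3 to 8, for responder rates from 5% to 50%. The documents give no distribution for either endpoint, so the power figures only show that a shared shift favours the continuous measure strongly and a minority response does not. It does not follow that the trial would miss moderate effects in general, that the categories should be replaced, or that between-arm modelling such as ANCOVA is required. The sample size is unaffected.

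Separately, the PSA cut is not consistent: 2.4.3 and 8.5.3 use 30%, whereas 7.1.3 uses 50%. Those sections must be reconciled whichever summary is reported.

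**What to change.** In section 8.5.3:

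- **PSA.** For men with both values, report per arm the geometric mean of pre-prostatectomy PSA divided by screening PSA, with a 95% CI, and show individual percent changes. Keep the ≥30% proportion beside it.
- **PD-L1.** Record percent staining when the slides are read. For each arm and location, report the median within-patient change, with a signed-rank test labelled exploratory. Keep the 0-3 shift table.

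The cost is a change of SAP wording, one extra data field and a few more exploratory outputs. No extra patients, samples or visits are needed. The downside is the lower reproducibility of percent staining, which is why the score remains. The field should be added before slides are read, because recovering the percentage later would mean reading them again.

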## 8.5 Analyses Plans

Safety analyses will be performed on safety-evaluable patients, defined as enrolled patients who received any amount of the study treatment. Efficacy analyses will be performed on efficacy-evaluable patients, defined as safety evaluable patients with measurable disease at baseline.

Demographic and baseline characteristics will be summarized by arm and overall. In general, frequency distribution and percentage will be used to summarize categorical measurements, while mean (with standard deviation) and median (with range) will be used to describe symmetric and skewed continuous measurements, respectively. Univariate analysis among variables will be assessed using the two-sample t-test, Wilcoxon-rank-sum test, Chi-square test, as appropriate.

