### 8.5.1 Primary Analysis (or Analysis of Primary Endpoint)

The primary analysis for immune response within the prostate will include all enrolled subjects who receive at least 1 dose of PROSTVAC or ipilimumab in any of the treatment arms, and undergo RP. Analysis will be done for each arm separately as well as aggregate for all treatment arms.

CD3+ T cell infiltration will be assessed by IHC staining, and quantitated by the number of CD3+ T cells/ $\mu\text{m}^2$ . Therefore, the number of T cells will be normalized per unit area. For the analysis of the primary endpoint, T cells will be enumerated from tumor/benign tissue interface (from here on referred to as the “tumor interface”). Subjects will be considered to have a “positive” response if they exhibit a  $\geq 2$ -fold increase in CD3+ T cell infiltration, and a “negative” response if they exhibit a  $< 2$ -fold increase. The proportion of patients who have “positive” responses will be reported, with 95% confidence intervals. Furthermore, the positive response rate will be compared between the combination arm vs. the monotherapy arms (pooling the two monotherapy arms together) via two-sample proportion test. Pairwise comparisons among the three arms will also be performed by two-sample proportion test. No multiple testing adjustments will be performed. Additional analyses will be performed for assessment of response at the tumor center and benign glands and will be reported similarly to the primary endpoint.

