### 8.5.2 Secondary Analyses (or Analyses of Secondary Endpoints)

- T cell tumor infiltration (of selected T cell subsets) will be scored by IHC assessment, and scored by the number of T cells/ $\mu\text{m}^2$ . Therefore, the number of T cells will be normalized per unit area. The change in T cell infiltration following neoadjuvant therapy will be determined as described above for the primary endpoint. Similar analyses may be performed for other immune cells, such as CD4+, CD8+, CD56+, FOXP3, etc. Results will be reported as described for the primary endpoint, and T cell infiltration will be reported separately for areas of tumor interface, tumor center and benign tissue.
- Flow cytometry will be performed in both pre- and post-treatment peripheral blood mononuclear cells (PBMC) to determine the change in T cell activation (both  $\text{T}^{\text{reg}}$  and  $\text{T}^{\text{effector}}$  cells) after neoadjuvant therapy. Descriptive statistics for continuous measurements will be used to summarize the changes.
- Treatment-related toxicities will be assessed according to NCI CTCAE v4.03, for all patients who receive at least a single dose of investigational therapy. The distribution for the

maximum observed grade for each adverse event will be tabulated and reported with 95% confidence interval.

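### The exploratory PD-L1 comparison between locations of one prostate names a proportion test with no pairing and no cut-off; on its natural reading it loses power but does not inflate false positives (minor)

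*Combined protocol and SAP*

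**What the plan says.** Section 8.5.3 sets out the PD-L1 analysis in four steps.

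- Scale: "PD-L1 expression, by IHC assessment, will be scored on a 0-3 scale".
- Unit: "For each subject, the change in PD-L1 expression score following neoadjuvant therapy will be calculated".
- Summary: "Descriptive statistics for categorical measurements will be used to summary the PD-L1 expression change for each location".
- Test: "univariate analysis (proportion test) will be applied to explore the PD-L1 expression score change between locations".

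The PD-L1 text does not list the locations. The nearest list is in section 8.5.2: "T cell infiltration will be reported separately for areas of tumor interface, tumor center and benign tissue". It also gives no cut-off for the score change, no significance level, and no statement on whether the three arms are pooled.

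Two other places in section 8.5 bear on what the test means. The general paragraph says: "Univariate analysis among variables will be assessed using the two-sample t-test, Wilcoxon-rank-sum test, Chi-square test, as appropriate". Section 8.5.1 says of the arms: "Pairwise comparisons among the three arms will also be performed by two-sample proportion test".

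**The concern.** Each patient contributes a score change at more than one location, so the comparison between locations is within patients. A two-sample proportion test treats the locations as separate groups of people. Its standard error omits the covariance between locations and is too large when that covariance is positive.

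A change from -3 to +3 is also not a proportion until someone decides what counts as an increase. Without a cut-off fixed in advance, that decision may be made after the data are seen, and any cut-off discards the size of the change.

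What is at stake is limited. A real difference in PD-L1 change between locations could be missed, and a null result could be read as evidence that the locations behave alike.

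**Working it through.** **The plan's own figure.** There is none. Section 8.2 gives power and precision only for CD3+ response. Its 13 evaluable patients per arm (3 × 13 = 39; 39/0.93 = 41.9, hence 42 accrued) supply the two sample sizes used here: 13 for one arm and 39 with arms pooled. Using them for PD-L1 is an assumption.

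**Step 1: which test is meant.** The PD-L1 sentence says neither paired nor unpaired. The general paragraph of section 8.5 illustrates univariate analysis with independent-sample tests only. Section 8.5.1 uses the two-sample form of the proportion test. No McNemar, signed-rank or Friedman test appears anywhere in section 8.5. The two-sample reading is therefore the natural one, but it is inferred.

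**Step 2: size of a two-sample test on paired proportions.** Let p be the proportion with an increase at each of two locations, and φ the within-patient correlation of that yes/no outcome.

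- True variance of the difference: 2p(1−p)(1−φ)/n.
- Variance used by the two-sample test: 2p(1−p)/n.
- Large-sample size at nominal two-sided 5%: 2[1 − Φ(1.96/√(1−φ))].

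| φ | 1.96/√(1−φ) | Actual size |
|---|---|---|
| −0.2 | 1.79 | 7.4% |
| 0 | 1.96 | 5.0% |
| 0.3 | 2.34 | 1.9% |
| 0.5 | 2.77 | 0.6% |
| 0.7 | 3.58 | 0.03% |

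Under positive correlation the test is conservative. Only negative correlation would inflate its size.

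**Step 3: power with a yes/no outcome.** Assumed rates are 45% and 20%, at two-sided 5%, with 200,000 replicates.

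| n | φ | Two-sample | McNemar, large-sample | McNemar mid-p |
|---|---|---|---|---|
| 39 | 0 | 67% | 66% | 64% |
| 39 | 0.3 | 70% | 80% | 80% |
| 39 | 0.5 | 73% | 95% | 94% |
| 13 | 0 | 30% | 25% | 21% |
| 13 | 0.3 | 27% | 34% | 22% |
| 13 | 0.5 | 23% | 40% | 21% |

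With no correlation, pairing gains nothing. At 13 patients mid-p McNemar never beats the two-sample test.

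**Step 4: power with the ordinal change kept.** Assumptions: a latent normal variable at each location, cut into score changes; a shift of 0.6 SD; latent correlation 0.5 to 0.7; two-sided 5%. For a cut at the median, a latent correlation r gives φ = (2/π)·arcsin(r). So r = 0.5 gives φ = 0.33, and r = 0.7 gives φ = 0.49. By the step 2 formula the sizes are 1.6% and 0.6%, in line with the simulated 0.6-2.0% at 39 patients.

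| n | Two-sample proportion | McNemar mid-p | Signed-rank |
|---|---|---|---|
| 39 | 48-58% | 58-80% | 83-98% |
| 13 | 13-22% | below the two-sample test | 32-57% |

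**Step 5: where the gain comes from.** Take one case at 39 patients, correlation 0.5, with 31% and 54% showing an increase. Power is 56% two-sample, 69% McNemar mid-p and 92% signed-rank. Of the 36-point gain, 69 − 56 = 13 points come from pairing and 92 − 69 = 23 from keeping the ordinal scale. If most scores do not change (16% and 35% with an increase), the figures are 50%, 60% and 70%. The signed-rank advantage thus depends on the score distribution and can fall below the range in step 4.

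**The case against.** The strongest reply is that the plan is under-specified rather than wrong. McNemar's test is also a test of proportions. Where the authors mean a two-sample test in section 8.5.1, they say so. The general paragraph allows for choosing the test to suit the data. Section 8.5.3 itself uses mixed models with subject as a random effect for antigen-specific T-cell immunity, so the authors know how to handle dependence within patients. This stands in part: the documents do not support the reading that the plan prescribes an unpaired test. But no paired test is offered, and an analyst following the text would most likely run a two-sample one. The missing cut-off remains on either reading.

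The second reply is that the error is on the safe side and nothing depends on it. That also stands. A reader might infer a raised risk of false positives; under positive correlation the opposite holds. A reader might also infer that pairing alone accounts for the whole power gap; step 5 shows that it does not.

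The third reply is that at 13 patients even signed-rank reaches only 32-57%, so a difference of this size could well be missed whatever test is used. That is true of analysis by arm and much less so of a pooled analysis. It is one reason to state which is intended.

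**Conclusion.** The point holds as a minor one. As naturally read, section 8.5.3 ignores the pairing of locations within a patient and reduces an ordinal change to a proportion with no stated cut-off. The consequence is lost power: roughly 48-58% against 83-98% at 39 patients, and 13-22% against 32-57% at 13. These figures assume a latent correlation of 0.5 to 0.7, a 0.6 SD shift, two-sided 5% and particular score thresholds. The documents give none of these, so the direction is firmer than the size. With zero correlation the benefit of pairing disappears, and only the benefit of keeping the ordinal scale can remain.

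A reader might take this as a threat to the trial's main result. It is not: PD-L1 change is an exploratory endpoint in section 2.4.3, and the CD3+ primary endpoint and the sample size do not depend on it.

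**What to change.** In section 8.5.3:

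1. Replace the proportion test with a paired analysis of the within-patient difference in score change: Wilcoxon signed-rank for two locations, Friedman for three.
2. Name the locations for PD-L1. If they are the three listed in section 8.5.2, say so.
3. State whether the comparison is made within each arm or with arms pooled.
4. Report the paired difference with its confidence interval, and label the result exploratory.
5. If a proportion is still wanted, define in advance what counts as an increase, and use McNemar for two locations or Cochran's Q for three. Note that mid-p McNemar gives no power gain at 13 patients per arm.

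The cost is a few sentences of wording. No new tissue, staining or patients are needed.

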Secondary Objectives	
 
To characterize T cell subsets and NK cells infiltrating the prostate after neoadjuvant administration of PROSTVAC OR ipilimumab OR the combination.
 
To measure the treatment-induced effects on circulating T cells following neoadjuvant PROSTVAC OR ipilimumab OR the combination of PROSTVAC and ipilimumab.
 
To assess the safety of PROSTVAC OR ipilimumab OR the combination in the neoadjuvant setting.
 

Exploratory Objectives	
 
To examine the effects of neoadjuvant PROSTVAC OR ipilimumab OR the combination on systemic antigen-specific immune responses.
 
To assess various immune monitoring parameters of cellular and humoral immune response following neoadjuvant PROSTVAC OR ipilimumab OR the combination in blood and in the tumor.
 
To determine the impact of neoadjuvant PROSTVAC OR ipilimumab OR the combination on PD-L1 expression in patients with localized PC.
 
To determine the clinical benefit of neoadjuvant PROSTVAC OR ipilimumab OR the combination in patients with localized prostate cancer measured by: 
 
PSA response
 
Pathologic response
 
 
 

Study Design	Open label randomized phase II trial of PROSTVAC and Ipilimumab prior to RP. There will be three arms in the study: 1) PROSTVAC alone, 2) Ipilimumab alone, 3) PROSTVAC + ipilimumab. To compare the immune response following treatment, tissue from the prostatectomy specimen will be compared with tissue from the core biopsy specimen obtained prior to treatment, with each subject serving as his own control. The immune response of each arm as well as in aggregate will be compared with a reference control group. Figure 1 presents a schematic of the study design.
Number of patients	42 (14 patients in each arm)
Duration of Therapy	Patients will be randomized to receive PROSTVAC or ipilimumab alone, or the combination of PROSTVAC and ipilimumab, and will undergo RP 12 weeks after start of therapy.
Duration of Follow up	All subjects will be followed for 1 year following RP.
Duration of study	The study will conclude when all enrolled patients have been followed for 1 year following RP. The estimated duration of study, from start of enrollment to final study report is 2 years.

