### 3.3.1 Inclusion Criteria

For a subject to be eligible for participation in this study, *all* of the following criteria must be satisfied:

1. Patients must have histologically confirmed adenocarcinoma of the prostate without previous therapy for PC.
  - a. Treatment-naïve AND
  - b. Undergoing RP as initial, locally definitive therapy for PC AND
  - c. Eligible for RP in a 3 month timeframe AND
  - d. Able to consent for RP
2. Subject's archival prostate biopsy specimen is available, and subject consents to provide tissue for study endpoint analysis. The prostate biopsy slides or blocks must be available prior to starting any study treatment.
3. Age  $\geq$  18 years
4. Subject has an Eastern Cooperative Oncology Group (ECOG) performance status of 0 or 1 (Appendix 1).
5. Subject has adequate organ function, defined as:
  - a. White blood cell (WBC) count  $\geq$  3,000/mcL
  - b. Absolute neutrophil count (ANC)  $\geq$  1,500/mcL
  - c. Platelet count  $\geq$  100,000/mcL
  - d. Hemoglobin (Hgb)  $\geq$  10.0 g/dL
  - e. Creatinine  $\leq$  1.5x institutional ULN
  - f. Total bilirubin  $\leq$  1.5 x institutional ULN
  - g. Alanine aminotransferase (ALT)  $\leq$  1.5 x institutional ULN
  - h. Aspartate aminotransferase (AST)  $\leq$  1.5 x institutional ULN
6. No known history of human immunodeficiency virus (HIV) 1 and 2, human T-cell lymphotropic virus (HTLV)-I/II, and Hepatitis B and C.
7. Ability to understand a written informed consent document, and the willingness to sign it.
8. Because of the unknown potential risk to a gamete and/or developing embryo from these investigational therapies, subjects must agree to use adequate contraception (i.e. barrier method) for the duration of study participation, and for three months after discontinuing therapy.

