# 7 Reporting and Documentation of Results

## 7.1 Evaluation of Activity

### 7.1.1 Primary endpoint: Immunohistological Characterization of CD3+ T Cell Infiltration within Prostate Tissue.

The primary endpoint response measure will be the change in the number of infiltrating CD3+ T cells/ $\mu\text{m}^2$  within the prostatic tumor tissue from the diagnostic core biopsy specimens to the post-treatment prostatectomy tissue specimens, based upon IHC analysis. The infiltrate will be scored by the number of CD3+ cells/ $\mu\text{m}^2$ . Thus, the number of inflammatory cells will be normalized to the unit area. Both biopsies and RP specimens will be quantitated with this frequency. For each patient, the change in the number of CD3+ T-cell infiltration from the pre-treatment biopsy to post-treatment prostatectomy tissue specimens will be represented by the ratio of post-treatment prostatectomy tissue specimens vs. pre-treatment biopsy.

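### The count of clonotypes in the top 25% of reads depends on T-cell input, and section 8.5.3 compares it between biopsy and prostatectomy with no equalisation of that input

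*Combined protocol and SAP*

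**What the plan says.** The last item of section 8.5.3 compares the tumor repertoire before treatment and at prostatectomy, for each treatment taken singly. The measure of change is a raw count, described as "calculating the number of unique clonotypes comprising the top 25th percentile of cumulative reads after sorting by clone abundance". The Abstract (Study Design) identifies the two tissues: "tissue from the prostatectomy specimen will be compared with tissue from the core biopsy specimen obtained prior to treatment". The biopsy is archival. Section 3.3.1 requires that "Subject's archival prostate biopsy specimen is available", with no minimum amount of tissue or DNA.

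The tumor part of the analysis is optional: "The responses in the tumor may also be evaluated in prostate biopsy samples to allow correlation with responses in the periphery". A second measure is named separately: "Repertoire change between sequencing experiments will be measured using Morisita's distance".

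Neither section 2.4.3 nor section 8.5.3 gives a rule on template number, DNA amount, read depth, down-sampling or minimum input for sequencing. The immunohistochemistry counts are treated differently. Section 8.5.1 says: "Therefore, the number of T cells will be normalized per unit area". The 12 untreated reference patients in section 8.6 lie outside the section 8.5 analyses, so they are not specified as a check on biopsy-to-prostatectomy differences in this count.

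**The concern.** The number of clonotypes needed to reach a quarter of the reads is not a property of the repertoire alone. With few templates, most clones are seen once, and chance duplicates decide which come first. As more templates are sampled the count climbs toward its true value. Two specimens from the same repertoire can therefore give different counts because one supplied more T cells.

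The plan's hypothesis (section 1.4) is that effective immunotherapy recruits T cells to the tumor. If so, the post-treatment specimen tends to hold more templates even when the same amount of tissue is sequenced. The artefact would then move with the primary endpoint. A higher count reads as a broader, less clonal repertoire, so a true expansion of a few clones could be hidden or appear with the wrong sign.

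**Working it through.** The plan states no figure for this analysis, so there is none to reproduce. The check asks what the planned count does when nothing changes biologically.

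**Inputs.** From the documents: the counting rule (8.5.3) and the two tissue types (Abstract). Assumed, because the documents are silent: template numbers, repertoire size and repertoire shape.

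**Limiting case.** If all N sampled templates are distinct, a quarter of them are needed to reach 25%, so the count is N/4. For N = 300 this is 75; for N = 3,000 it is 750. The ratio equals the input ratio, 10.

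**Simulation with no treatment effect.** One fixed repertoire of 20,000 clones has clone k with frequency proportional to k^(-a). Draw 300 templates (biopsy) and 3,000 (prostatectomy) by multinomial sampling, sort by abundance, and count the clones needed to reach 25% of the sample. Then down-sample the 3,000 to 300 without replacement and count again. Mean counts:

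| Exponent a | Biopsy, 300 | Prostatectomy, 3,000 | Ratio | Prostatectomy down-sampled to 300 |
|---|---|---|---|---|
| 0.6 | 65 | 272 | 272/65 = 4.2 | 65 |
| 0.8 | 36 | 75 | 75/36 = 2.1 | 36 |
| 1.0 | 7.1 | 7.7 | 7.7/7.1 = 1.1 | about 7 |
| 1.2 | 2.0 | 2.0 | 1.0 | 2.0 |

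If the inputs are swapped, the ratios invert: at exponent 0.8, 36/75 = 0.48, a spurious fall.

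**Other shapes and a smaller imbalance.** With 200,000 clones and 300 against 3,000 templates, the count rose in all null pairs for four diverse repertoires (power-law exponents 0.5 and 0.7; lognormal SD 1.5 and 2.5), by 2.1- to 9.3-fold. At exponent 1.0 it rose in 77% of pairs, by 1.2-fold. Where a few clones already held 25%, it rose in 3% to 8% of pairs, with a ratio near 1.0. With only a threefold imbalance (1,000 against 3,000), the four diverse repertoires gave ratios of 1.28 to 2.84. After down-sampling to equal templates, the ratio was 0.97 to 1.03 in every scenario.

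**Equal read depth is not enough.** With 100,000 reads for each specimen (20,000 clones, exponent 0.8), the counts were still 34 against 77. Reads are copies of the templates, so more reads do not restore clones that were never sampled.

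**Masking.** At exponent 0.8, let 20 clones gain 10% of the repertoire after treatment. The planned count rose from 36 to 44, and rose in 88% of pairs. Down-sampled to 300 templates, it fell from 36 to 28, and fell in 86% of pairs. With a 15% gain the planned count did fall, from 35 to 30, but by less than the down-sampled count, which reached 23. Masking also depends on which clones expand: if they are already the largest, the planned count falls even at a 10% gain.

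**The case against.** The strongest reply is that size and direction both rest on assumed inputs. No section gives a template number, DNA amount or read depth. A prostatectomy specimen is larger than a core, but that does not fix the aliquot sequenced. If that aliquot held fewer T cells, the bias would run the other way, and in a skewed repertoire there is almost none. This stands, and it limits the point to what can happen when the repertoire is diverse and inputs differ.

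An input rule may also sit in the Laboratory Manual, to which Tables 3 and 4 refer for immune-monitoring collection and which is not available here. That is possible. The supportable statement is that the analysis section gives no rule. A rule equalising tissue or DNA alone would also leave template numbers unequal if T-cell density changes.

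A reader might infer three stronger claims that the documents do not support:

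- That every arm will look more diverse after treatment. This would need a diverse repertoire and a larger prostatectomy input in every arm, and neither is documented.
- That arms will be wrongly declared to differ in clonality. Section 8.5.3 takes each treatment singly and specifies no between-arm test of this count, so that misreading could come only from informal comparison.
- That the second measure has the same fault. The plan names Morisita's measure, and the sample-size-corrected Morisita index stayed at 0.99 to 1.06 for two unequal samples of one repertoire. The Morisita-Horn variant does behave poorly, but the plan does not name it.

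**Conclusion.** The point holds in conditional form. The planned count is sensitive to T-cell input, and section 8.5.3 does not equalise that input between two specimens that may well differ in it. Under the assumed 300 against 3,000 templates, the spurious change ranges from nil to about 4.2-fold over exponents 0.6 to 1.2 with 20,000 clones. It is larger for flatter, larger repertoires and reverses if the prostatectomy input is the smaller. The size in this trial cannot be known from the documents.

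The importance is minor. The tumor analysis is exploratory and optional, and no stated decision rests on it. The primary CD3 endpoint and the sample size do not use this count. The reason to act is that, if the analysis is run, the direction of the reported change could be wrong, and a rule fixed beforehand avoids a choice made after seeing the data.

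**What to change.** In section 8.5.3:

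- Before counting clonotypes in the top 25%, down-sample each patient's biopsy and prostatectomy data to the smaller of the two T-cell template counts (templates, not reads), and average the count over repeated draws.
- Preset a minimum template number below which a pair is not analysed.
- Report the template count for each specimen.
- If the assay does not yield template counts, report the clonotype count as descriptive only, with a measure of T-cell input beside it, and draw no conclusion about the direction of change in clonality.

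The cost is a few sentences in the plan and, where template counts exist, a short program. The documents do not say whether they will exist, hence the last item. The downside is that some prostatectomy data go unused and patients with very small biopsies drop out of this analysis.
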